4 INVESTIGATIONAL PLAN

4.1 Study Design

This is a Phase 1, single center, open label, non-randomized, crossover, mechanism of action study, using a surrogate marker for contraceptive efficacy (the Standardized Postcoital Test, PCT) to assess the mechanism of action and contraceptive potential of the ZB-06 film.

The product to be tested is the ZB-06 vaginal film, containing 20 mg of the HC4-N anti-sperm antibody. Participants will be women who are not at risk for pregnancy due to surgical sterilization, and their male sexual partners. The individual evaluating the cervical mucus for midcycle characteristics and presence of sperm will be blinded as to the treatment cycle. Each participant will be seen in approximately ten visits, over a period of 3 - 6 months. Volunteers will be consented at Visit 1 and undergo procedures to confirm they are eligible to continue in the study. Each participant will undergo three PCT cycles. The first PCT cycle will be a baseline cycle, done without the use of any product, in order to demonstrate the participant's ability to undergo normal ovulatory events and to produce receptive, midcycle cervical mucus. The male partner's ability to produce motile sperm capable of penetrating the cervical mucus is also evaluated in this baseline cycle. A product use PCT cycle will be carried out during the subsequent menstrual cycle using the ZB-06 film. An additional PCT cycle without product will be carried out during the subsequent menstrual cycle. Cycles may need to be repeated depending on the characteristics of the cervical mucus and the number of sperm found in the vaginal pool and endocervical specimens (see Appendix B).

The primary endpoint will be an assessment of the potential contraceptive activity of the ZB-06 film using a surrogate assessment for contraceptive efficacy, i.e., observing the degree to which progressively motile sperm can be excluded from the endocervical mucus.

At ovulation, the participant's cervical mucus will be assessed by Insler scoring. Once adequate cervical mucus is documented to be present, the couple will have unprotected intercourse within approximately 24 hours of the cervical mucus check. Two to three hours after intercourse, the participant's vaginal fluid and cervical mucus will be evaluated for the presence of sperm (motile, immotile). The expectation is that at baseline, participants will have an average of greater than 5 motile sperm per high power field (HPF), averaged over 9 HPFs, and that with the use of the ZB-06 film, participants will on average have at least a 10-fold reduction in motile sperm per HPF, averaged over 9 HPFs.

The secondary objective will be assessed at each visit, by querying participants regarding any treatment-emergent adverse events (TEAEs). TEAEs from the male sexual partner will be assessed at each visit, per the female participant's report or from the male directly. The male partner will be interviewed for TEAEs by phone within 72 hours of intercourse with product. Safety will also be assessed by comparing the concentrations of cervicovaginal (CV) mucosal cytokines and chemokines with and without ZB-06 film use.

Finally, an estimation of the *in vivo* pharmacokinetics of HC4-N will be described in serum cervical mucus, and CV fluid. Our expectation is that serum levels of ZB-06 will be very low to unquantifiable, while CV fluid levels will be high, supporting local activity of the product.

A listing of all study procedures and sampling is provided in the Schedule of Events Table in Appendix A.

4.2 Selection and Withdrawal of Subjects

- 4.2.1 Inclusion Criteria:
 - Age 18 50 years, inclusive
 - General good health, by volunteer history and per investigator judgment
 - History of regular menstrual cycles of 21 35 days (inclusive), by volunteer report
 - History of a normal PAP smear or ASCUS with negative HPV testing within the previous 12 months
 - Willing to abstain from intercourse and use of vaginal medications, lubricants, and other products as required in the protocol
 - Willing to use non-spermicidal, lubricated condoms for any vaginal intercourse from the first day of each menstrual cycle until 72 hours before expected midcycle
 - In a mutually monogamous relationship with a male partner who:
 - Is at least 18 years old
 - Has no known risk for sexually transmitted infections (STIs)
 - Is willing and able to comply with protocol requirements including sexual activity/ abstinence and condom use requirements
 - Can engage in vaginal intercourse with the participant, with and without condoms, as specified in protocol
 - Is not taking exogenous hormones (e.g. testosterone)
 - Protected from pregnancy by female surgical sterilization
 - Vaginal and cervical anatomy that, in the opinion of the investigator, lends itself to easy genital tract sample collection
 - Willing to give voluntary consent, sign an informed consent form and comply with study procedures as required by the protocol
- 4.2.2 Exclusion Criteria:
 - History of hysterectomy
 - Surgical sterility or known history of infertility in male partner

- Sterility or known history of sperm dysfunction in male partner
- Currently pregnant by urine pregnancy test at the enrollment visit, or within two calendar months from the last pregnancy outcome. *Note: If recently pregnant must have had at least two spontaneous menses since pregnancy outcome*
- Current use of any hormonal contraceptive or a copper or hormonal IUD, or use of Depo-Provera in the last 120 days
- Currently breastfeeding or having breastfed an infant in the last two months, or planning to breastfeed during the course of the study
- Significant gynecological abnormalities (including abnormal vaginal bleeding, excessive vaginal discharge, or vulvar/vaginal pain or irritation)
- Current UTI, vaginal candidiasis, or symptomatic bacterial vaginosis
- History of sensitivity/allergy to ZB-06 film components, for either the volunteer or her male partner
- In the last three months, either the volunteer or her male partner diagnosed with or treated for any STI or pelvic inflammatory disease, or either partner with known risk factors for sexually transmitted infections. *Note: Women with a history of genital herpes or condylomata who have been asymptomatic for at least six months may be considered for eligibility*
- Positive test for *Trichomonas vaginalis, Neisseria gonorrhea, Chlamydia trachomatis,* or HIV at the screening visit
- Deep epithelial genital findings such as abrasions, ulcerations, and lacerations, or vesicles suspicious for an STI
- Known current drug or alcohol abuse which could impact study compliance
- Participation in any other investigational trial within the last 30 days or planned participation in any other investigational trial during the study
- History of gynecological procedures (including genital piercing) on the external genitalia, vagina or cervix within the last 14 days
- Abnormal finding on laboratory or physical examination or a social or medical condition in either the volunteer or her male partner which, in the opinion of the investigator, would make participation in the study unsafe or would complicate interpretation of data

4.2.3 Withdrawal of Subjects

Participants who sign the informed consent and agree to participate in the study, but do not meet eligibility criteria prior to undergoing the initial cervical mucus check (Visit 2) will not continue in the study. No electronic case report forms (eCRFs) will be completed for participants who do not undergo the cervical mucus check at Visit 2.

Once a participant undergoes Visit 2 procedures, she may be withdrawn from the study for the following reasons:

- Inability to achieve adequate cervical mucus in two attempts at the baseline cycle
- Inadequate sperm in endocervical aspirate during baseline testing, despite adequate mucus and presence of sperm in vaginal pool
- Medical reasons, including diagnosis of an STI (in the participant or her partner) or any intercurrent illness that would jeopardize the participant's health or the interpretation of the results of the study
- Failure to follow protocol requirements that is judged severe enough by the investigator to significantly affect study outcomes
- Pregnancy
- Any AE, laboratory abnormality, or intercurrent illness which, in the opinion of the investigator, indicates that continued participation in the study is not in the best interest of the subject
- Personal reasons (participant request)
- Discontinuation of entire study

4.2.4 Replacement of Subjects and or Repeat of Product Use Cycle

Approximately 15 women will complete the study. Participants who discontinue early may not re-enroll. Participants who discontinue may be replaced as needed to achieve the desired full 15 women completing both a baseline and a product PCT cycle. Participants who have a failed product use cycle, due to factors such as but not limited to: erectile dysfunction, inability to ejaculate, illness, etc., may repeat the product use cycle with a second dose of the 20 mg film, in a subsequent menstrual cycle

4.3 Randomization and Blinding

This is an open-label cross-over study, and neither randomization nor blinding of the participant or the investigator will be employed. The individual evaluating the cervical mucus for quality (Insler score) and the presence or absence of motile sperm in cervical mucus and the vaginal pool will be blinded to the study cycle and use or non-use of the study product.

4.4 Prior and Concomitant Medications and illnesses

Prohibited medications include use of intravaginal products within 72 hours of the expected midcycle date, as well as all hormonal contraceptives and presence of or treatment for STIs. All concomitant medications will be recorded on CRFs.

5 STUDY DRUG MANAGEMENT

5.1 Study Drug Formulation

The ZB-06 drug product is a vaginal film containing 20 mg of the HC4-N drug substance and additional excipients as described in Table 1.

Table 1: ZB-06 Product Composition Unit Dosage	Form
--	------

Component	Function	Target Quantity per film		
Antibody HC4-N Drug Substance	Active Ingredient	20 mg		
Maltitol	Stabilizer	54 mg		
Histidine	Stabilizer	4.2 mg		
Polysorbate 20	Surfactant	13 µg		
PVA 8-88	Polymer Base	126 mg		

5.2 Study Drug Packaging and Labeling

The ZB-06 film is packaged in a sealed foil laminate pouch. A representative version of the label affixed to the pouch is reproduced below as Figure 1:

Figure 1: ZB-06 Film Package Label

Manufactured for ZabBio, Inc. [name]	ZB-06 Film for Vaginal Application					
[name] by	Lot: 19ZB06-001 Storage: 2-8°C					
Kentucky Bioprocessing, Inc	Conc: 20 mg HC4-N Qty: 1 film					
[name]	D.O.M: 07 NOV 2019					
Caution-New Drug Limited by United States law to investigational use.						

5.3 Study Drug Handling and Storage

The packaged ZB-06 drug product will be shipped and stored at 2-8° C until dispensed to the study participant.

5.4 Study Drug Administration

Participants will insert one ZB-06 film intravaginally approximately 30 minutes prior to sexual intercourse during the product PCT cycle. The film is inserted digitally high in the vagina after folding it the participant's finger.

5.5 Study Drug Accountability Procedures

The ZB-06 film will be stored in a temperature-monitored, access-controlled refrigerator at 2-8 $^{\circ}$ C until dispensed by the study staff to the participant at the product cycle cervical mucus check (CMC) visit (Visit 6). A log of receipt and dispensing will be kept by the study staff. Unused films will be returned to the Sponsor after study completion.

6 MEASUREMENTS AND EVALUATIONS

6.1 Efficacy Assessments

The primary method of evaluating preliminary effectiveness (primary objective) for the ZB-06 film will be the average number of progressively motile sperm (PMS) in aspirated endocervical mucus examined across 9 high powered fields (HPFs) at 400X magnification at 100 um sample chamber depth, in the ZB-06 treatment cycles comparted to the no product treatment cycles.

The mean, median, standard deviation, and interquartile range (IQR) of each woman's average number (across 9 HPFs) of progressively motile sperm per HPF will be calculated separately for baseline and each test PCT. Qualitative assessments of change from baseline, if any, will be based on the median and IQR, because of expected non-normality of test cycle data.

6.2 Safety Assessments

Tables and listings will be created for all TEAEs, defined as those occurring on or after first product use. However, the primary evaluation of safety will be the subpopulation of safety AEs that are urogenital, product-related, and/or serious. Data will be presented by presence of ZB-06 film according to relatedness of the finding to study product, whether AEs had onset before or after intercourse, and noted by gender, and the severity/seriousness of the AE.

In addition, concentrations of cytokines and chemokines will be described at baseline and after ZB-06 film use, as a surrogate of subclinical safety endpoints. Safety bloods (hematology, and metabolic panel) will be obtained at screening at Visit 8. Urinalysis will be done at the times indicated in the Schedule of Events (Appendix A)

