	6.	Sperm agglutination titer in serum by endpoint dilution measured at baseline, and 24 hours and 1 month after exposure to ZB-06 film
	7.	Concentrations of immune mediators in cervicovaginal lavage, measured via multiplex assays before and 24 hours after intercourse with vs. without study product.
	8.	Vaginal pH at baseline and 24 hours after intercourse with vs. without study product.
	9.	Nugent Score at Visit 6 baseline and 24 hours after intercourse with study product.

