3.2 Study Endpoints

3.2.1 Primary endpoint:

Number of progressively motile sperm in aspirated endocervical mucus 2-3 hours after sexual intercourse using ZB-06.

3.2.2 Secondary endpoint:

Incidence of Grade 2 or greater adverse events in the participant and/or her male partner in the interval between Visit 4 (the baseline intercourse without product) and Visit 6, in comparison to the incidence of Grade 2 or greater adverse events in the interval between Visit 7 (intercourse with product) and Visit 9.

3.2.3 Exploratory endpoints:

- 1. Concentrations of anti-sperm-antibody in *vaginal fluid*, measured by ELISA at baseline, at 2-3 hours, and at 24 hours after intercourse with and without product use, and at 1 month after product use
- 2. Sperm agglutination titer in *vaginal fluid* measured by endpoint dilution at baseline, and at 2-3 hours and at 24 hours after intercourse with and without product use, and at 1 month after product use
- 3. Concentrations of anti-sperm-antibody in *endocervical mucus*, measured by ELISA at baseline, and at 2-3 hours and at 24 hours after intercourse with and without product use, and at 1 month after product use
- 4. Sperm agglutination titer in *endocervical mucus*, by endpoint dilution measured at baseline, and at 2-3 hours and at 24 hours after intercourse with and without product use, and at 1 month after product use
- 5. Concentrations of anti-sperm antibodies in *serum*, measured by ELISA at baseline, at 24 hours, and at 1 month after exposure to ZB-06 film
- 6. Sperm agglutination titer in *serum* by endpoint dilution measured at baseline, and 24 hours and 1 month after exposure to ZB-06 film
- 7. Concentrations of immune mediators in cervicovaginal lavage, measured via multiplex assays before and 24 hours after intercourse with and without study product.
- 8. Vaginal pH at baseline and 24 hours after intercourse with vs. without study product.
- 9. Nugent Score at Visit 6 baseline and 24 hours after intercourse with study product.

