- 6. Sperm agglutination titer in *serum* by endpoint dilution measured at baseline, and 24 hours and 1 month after exposure to ZB-06 film.
- 7. Concentrations of immune mediators in *cervicovaginal lavage* measured via multiplex assays at baseline and at 24 hours after intercourse with and without study product.
- 8. Vaginal pH at baseline and 24 hours after intercourse with vs. without study product.
- 9. Nugent Score at Visit 6 baseline and 24 hours after intercourse with study product.

The continuous variables described in the Exploratory Endpoint section will be analyzed as follows: For two time point comparisons, the Wilcoxon Signed Rank Test will be utilized; for three time point comparisons, mixed linear model analysis will be performed. If dependent variables are not normally distributed, they will be (natural) log transformed prior to mixed linear model analysis. A significant effect will be followed by Tukey-Kramer multiple comparison tests. The mixed linear model analysis accounts for missing values should some participants fail to return for the 1 month time point. Statistical significance will be assumed when p<0.05. All analyses will be performed with SAS (Version 9.4; SAS Institute Inc., Cary, NC, USA).

An equivalence test will be performed between the average number of PMS (across 9 HPF) in aspirated endocervical mucus 2-3 hours after sexual intercourse without study product at Baseline (Visit 4) versus the average number of PMS (across 9 HPF) in aspirated endocervical mucus 2-3 hours after sexual intercourse without study product one month following exposure to study product (Visit 10). The purpose of this test is to determine whether the postcoital PMS concentrations one month following product exposure are equivalent to baseline levels. The equivalence test will be performed utilizing the two one-sided t-tests (TOST) procedure.

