Appendix A. Schedule of Events

PROCEDURE	Visit 1 Screening	Visit 2 Enrollment	Visit 3 Baseline (No-product) CMC	Visit 4 Baseline (No-product) PCT	Visit 5 24 h safety check	Visit 6 Product CMC	Visit 7 Product PCT	Visit 8 24 h safety check	Visit 9 No-product CMC	Visit 10 No-product PCT and Study Exit
Informed consent	Х									
Confirm eligibility	Х	Х								
Dispense informed consent	v									
for male partner	Λ									
Enroll	~ ~	X								
History	X					N 7		N.		NY.
Adverse Event Collection	X	X	X	X	X	X	X	X	X	X
Log concomitant medications	Х	X	X	X	Х	X	Х	X	X	X
Condom and abstinence	Х	Х	Х	Х	Х	Х	Х	Х	Х	
Condom distribution	x				X			x		
Ovulation predictor kit	24									
distribution		Х			Х			Х		
Film insertion training/review	Х					Х				
Film dispensed						Х				
Urine pregnancy test	Х	Δ	Δ	Δ	Δ	Х	Δ	Δ	Δ	Δ
Urinalysis with reflex urine	v		v		v	v		v		
culture	Λ		Λ		Л	Λ		Λ		
NAATS for CT, GC,	х									
Trichomonas										
HIV blood test	X							37		
CBC, Metabolic Panel	X		V			v		X		
Vaginal pH	Δ	٨	X		٨	X		X A		
Slide for Nugart appring	Δ	Δ	Δ		Δ					
Pap	٨					Λ		Λ		
Serum for HC4-N ELISA					x	x	x	x	x	
Serum for sperm					Λ	Λ	Λ	Λ	Λ	
agglutination					Х	Х	Х	Х	Х	
Vaginal swab or aspirate for			v	V	v	v	v	v	v	V
and sperm agglutination assay			Л	А	Л	л	л	Л	Л	А
Endocervical aspirate for										
Insler score, sperm count and			37	37	37	37	37	37	V	37
motility, HC4-N ELISA,			Х	Х	Х	Х	Х	Х	Х	Х
sperm agglutination assay										
CVL for immune mediators			Х		Х	Х		Х	Х	
Vital signs	Х	Δ	Δ	Δ	Δ	Δ	Δ	Δ	Δ	Δ
Directed Physical exam	Х	Δ	Δ	Δ	Δ	Δ	Δ	Δ	Δ	Δ
Pelvic exam	Х		Х	Х	Х	Х	Х	Х	Х	Х
Colposcopy			Х	Х	Х	Х	Х	Х		
Woman's acceptability								X*		
questionnaire										
Man's acceptability								X**		
questionnane										

X Procedure done

 Δ Procedure done if indicated * Women's questionnaire administered at this visit.

**Men's questionnaire administered by telephone within 72 h of intercourse, and will include questions to elicit AEs.

Vaginal pool - any	- any Endocervix								
sperm present (including fragments) *	Mucus - adequate (thin)	No sperm	Some sperm but <5 progressively motile	≥5 progressively motile	Action at Baseline or Safety Cycle	Action at Test Cycle			
Yes	Yes	~			Similar results in test cycle would make				
Yes	Yes		✓		it appear that the product was successful.	Barrier successful			
No	Yes		✓		If this is safety cycle, may indicate	Continue to next cycle.			
Insufficient material	Yes		✓		induction of anti-sperm antibodies				

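### Section 6.2 states the cytokine safety comparison more loosely than Section 4.1 and endpoint 7, and Section 7.5.3 names no analysis that uses all four lavages

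*Combined protocol and SAP*

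**What the plan says.** Section 6.2 (Safety Assessments) says that "concentrations of cytokines and chemokines will be described at baseline and after ZB-06 film use, as a surrogate of subclinical safety endpoints". It gives no visit numbers, test or comparator.

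Section 4.1 states the safety comparison differently: "Safety will also be assessed by comparing the concentrations of cervicovaginal (CV) mucosal cytokines and chemokines with and without ZB-06 film use".

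Exploratory endpoint 7 names both conditions wherever it appears. Section 3.2.3 has "Concentrations of immune mediators in cervicovaginal lavage, measured via multiplex assays before and 24 hours after intercourse with and without study product". The Protocol Summary has "measured via multiplex assays before and 24 hours after intercourse with vs. without study product". Section 7.5.3 replaces the pre-coital sample with the word baseline: "measured via multiplex assays at baseline and at 24 hours after intercourse with and without study product".

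For all continuous exploratory endpoints, Section 7.5.3 gives one generic rule: "For two time point comparisons, the Wilcoxon Signed Rank Test will be utilized; for three time point comparisons, mixed linear model analysis will be performed". It does not say which visits or which contrast apply to immune mediators.

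The Appendix A row "CVL for immune mediators" has five marks. Read with Sections 6.5.3 and 6.5.5, they fall at Visits 3, 5, 6, 8 and 9.

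**The concern.** Every sample taken after film use is also a sample taken after unprotected intercourse, semen exposure and postcoital sampling. If baseline in Section 6.2 means the pre-coital sample of the film cycle (Visit 6), the change to Visit 8 mixes all of these. An inert film would look inflammatory if intercourse raises a mediator, and a real film effect could be cancelled if intercourse lowers it.

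The no-product cycle supplies the control, and endpoint 7 has a before/after by with/without structure. The analysis rule does not match that structure. A two-point test uses two of the four lavages and a three-point model uses three, so at least one cycle's own pre-coital value is left out, and the plan does not say which. With a multiplex panel tested at p<0.05, the contrast could be chosen after the data are seen. At stake is how readable the mucosal safety surrogate will be in a first-in-human study.

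**Working it through.** **1. What baseline means.** The Protocol Summary uses baseline for the whole no-product cycle (its reference-therapy row). The Nugent endpoint uses it for Visit 6, and says so. Section 6.2 uses it without a qualifier, so both readings are open.

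**2. The four lavages**

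| | Before intercourse | 24 h after |
|---|---|---|
| No-product cycle | Visit 3 | Visit 5 |
| Film cycle | Visit 6 | Visit 8 |

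Visit 9 adds a pre-coital lavage in the third cycle with no 24-hour partner, so it does not enter the film contrast.

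**3. What each contrast estimates.** On the log scale let w be a woman's level, c1 and c2 her cycle deviations (SD σc), e the visit error (SD σv), g the coital effect, d a drift from the first cycle to the second, and f the film effect:

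- V3 = w + c1 + e3
- V5 = w + c1 + g + e5
- V6 = w + c2 + d + e6
- V8 = w + c2 + d + g + f + e8

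| Contrast | Expected value | Variance |
|---|---|---|
| V8 − V6 | g + f | 2σv² |
| V8 − V5 | d + f | 2(σc² + σv²) |
| (V8 − V6) − (V5 − V3) | f | 4σv² |

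Adjusting V8 versus V5 for the own-cycle pre-coital values with slope β leaves f + (1 − β)d. Adjustment therefore removes g fully and d in part.

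**4. Size.** The plan has no figure to reproduce here: its only power statement (Section 7.2) concerns sperm counts, and it gives no mediator SD or coital effect. All of the following is assumed: n = 15 (Section 7.2), signed-rank test at two-sided 0.05, and f = 0.

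*Coital shift in units of the visit SD, with σc = 0 and d = 0 (20,000 runs):*

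| Coital shift | 0 | 0.25 | 0.5 | 0.75 | 1.0 | 1.5 |
|---|---|---|---|---|---|---|
| V6 vs V8 falsely significant | 4.9% | 9.1% | 24% | 46% | 69% | 96% |

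Over the same shifts, V5 vs V8 stays at 4.5-5.1% and the four-sample contrast at 4.6-5.2%. Hand check at 1.0 SD: the difference has mean 1 and SD √2 = 1.41, so 1/1.41 × √15 = 2.74 standard errors, in line with 69%.

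*Coital fold-change, with total within-woman log SD of 0.5 to 0.9 and d = 0:*

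| V6 vs V8 falsely significant | 1.5-fold | 2-fold |
|---|---|---|
| Variance split equally between cycle and visit | 36-82% | 77-100% |
| All variance at visit level | 19-53% | 47-92% |

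*Drift of 1.5-fold between cycles:* V8 vs V5 is falsely significant in 19-53% of trials over the same SD range. With σc = σv = 0.5 it is 29%, and the four-sample contrast stays at 5%. Hand check: ln 1.5 = 0.405, the SD is √(2 × (0.25 + 0.25)) = 1.00, and 0.405 × √15 = 1.57 standard errors.

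*Masking:* if intercourse halves a mediator and the film doubles it, then g + f = 0. With σc = σv = 0.5, V6 vs V8 flags the film in 5% of trials and the four-sample contrast in 69%.

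**5. Precision.** The four-sample contrast has smaller variance than V8 − V5 only when 4σv² < 2(σc² + σv²), that is, when σc > σv. If σc = 0, its variance is 4σv² against 2σv², so its SD is √2 = 1.41 times as large. Covariate adjustment estimates the slope and loses less, but at σc = σv the within-woman slope is 0.25/(0.25 + 0.25) = 0.5, so half of any log-scale drift remains. Neither contrast is best throughout, which is why one should lead and the other support it.

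**The case against.** A reader might infer that the plan will attribute coital effects to the film and leaves the no-product cycle unused. The documents do not support that. Section 4.1 says that safety is assessed by "comparing the concentrations of cervicovaginal (CV) mucosal cytokines and chemokines with and without ZB-06 film use", and endpoint 7 names both conditions in the Protocol Summary, Section 3.2.3 and Section 7.5.3. Baseline in Section 6.2 may itself mean the no-product cycle. Section 6.2 is also descriptive: it specifies no test and attributes no change to the film. The false-signal rates for Visit 6 versus Visit 8 therefore show what one possible reading would do, not what the plan prescribes.

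Two further points have force. Visit 8 versus Visit 5 is a two-point comparison that Section 7.5.3 already allows, and it is not distorted by a common coital effect. The endpoint is also exploratory: Section 6.2 rests the main safety evaluation on adverse events, the secondary endpoint compares adverse events between the two intervals, and no pause criterion in Section 9.1.1 uses a mediator.

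All of this stands, and it limits the point. It does not supply the missing contrast. Visit 8 versus Visit 5 is exposed to drift between cycles, which the collected pre-coital lavages could reduce, and no stated analysis uses them for that.

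**Conclusion.** The point holds in a limited form and at low severity. Section 6.2 is looser than Section 4.1 and endpoint 7, and permits a before/after reading that cannot separate film from intercourse and semen. Section 7.5.3 has no analysis matched to the four lavages, so own-cycle pre-coital values are not used as the design allows.

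The direction follows from the algebra. The error rates are illustrative, because they rest on assumed SDs, coital effects and drift. The fixed, non-randomised cycle order (Sections 4.1 and 4.3) remains a limit: if order alters the response to intercourse itself, that stays confounded with the film under every contrast considered here.

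**What to change.** - **Section 6.2:** align it with Section 4.1 by stating that mediators are compared with and without film, and give the visit numbers in place of the bare word baseline.
- **Section 7.5.3:** define the film contrast for each mediator, on the log scale and paired within woman, as the 24-hour value with film (Visit 8) versus without (Visit 5), each adjusted for its own-cycle pre-coital value (Visit 6, Visit 3). One mixed model with cycle as factor and own-cycle baseline as covariate does this. Give (V8 − V6) − (V5 − V3) as a supporting contrast.
- **Labelling:** state that the Visit 6 to Visit 8 change alone is descriptive and is not evidence of a film effect.
- **Limits to state:** the fixed cycle order, and the partial removal of drift by covariate adjustment.

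The cost is wording and analysis code; all four lavages are already scheduled. Adjustment may lose some precision if pre- and post-coital values correlate weakly, and a woman missing a lavage contributes less.
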